### 6.4.2 Criteria for Conditional Withholding of Amgen Investigational Product due to Potential Hepatotoxicity

For subjects who do not meet the criteria for permanent discontinuation of Amgen investigational product outlined above and have no underlying liver disease, and eligibility criteria requiring normal transaminases and TBL at baseline or subjects with

underlying liver disease and baseline abnormal transaminases, the following rules are recommended for withholding of Amgen investigational product:

- Elevation of either AST or ALT according to the following schedule:
  - Baseline AST or ALT value: Any AST or ALT elevation:  $> 8 \times \text{ULN}$  at any time
  - Baseline AST or ALT value: Any AST or ALT elevation:  $> 5 \times \text{ULN}$  but  $< 8 \times \text{ULN}$  for  $\geq 2$  weeks
  - Baseline AST or ALT value: Any AST or ALT elevation:  $> 5 \times \text{ULN}$  but  $< 8 \times \text{ULN}$  and unable to adhere to enhanced monitoring schedule
  - Baseline AST or ALT value: Any AST or ALT elevation:  $> 3 \times \text{ULN}$  with clinical signs or symptoms which are consistent with hepatitis (such as right upper quadrant pain/tenderness, fever, nausea, vomiting, or jaundice).
- OR: TBL  $> 3 \times \text{ULN}$  at any time
- OR: ALP  $> 8 \times \text{ULN}$  at any time

AMG 330 can be withheld pending investigation into alternative causes of DILI. If the investigational product is withheld, the subject is to be followed according to recommendations in [Appendix A](#) for possible DILI. Rechallenge may be considered if an alternative cause for impaired liver tests (ALT, AST, ALP) and/or elevated TBL is discovered and the laboratory abnormalities resolve to normal or baseline (Section [6.4.3](#)).

#### **6.4.3 Criteria for Rechallenge of Amgen Investigational Product After Potential Hepatotoxicity**

The decision to rechallenge the subject should be discussed and agreed upon unanimously by the subject, investigator, and Amgen.

If signs or symptoms recur with rechallenge, then the investigational product should be permanently discontinued. Subjects who clearly meet the criteria for permanent discontinuation (as described in Section [6.4.1](#)) should never be rechallenged.

#### **6.5 Concomitant Therapy**

Throughout the study, investigators may prescribe any concomitant medications or treatments deemed necessary to provide adequate supportive care except for those listed in Section [6.9](#). Concomitant therapies are to be collected from informed consent, through the EOS. For all concomitant therapies collect therapy name, indication, dose, unit, frequency, route, start date, and stop date.

Oxygen administration as supportive measure is permitted during study treatment.

Hydroxyurea for 7 days at a dose of [REDACTED] g / day is recommended prior to the first cycle of IP treatment for subjects with high WBC (> 15,000 cells/mcL). Administration of hydroxyurea after start of IP may be permitted after discussion with the Amgen medical monitor.

**COVID-19 vaccines are allowed per local standard of care for cancer patients.**  
**Vaccination procedure should be avoided during DLT period. COVID-19 vaccination should be documented as concomitant medication and vaccination-related adverse events should be recorded in the eCRF.**

Tocilizumab: Tocilizumab may be used to treat CRS as **clinically relevant and** described in [Table 7](#) below.

## **6.6 Specific Recommendations for Cytokine Release Syndrome, Tumor Lysis Syndrome and Infection Prophylaxis**

### **Cytokine Release Syndrome**

CRS is clinically defined and may have various manifestations. There are no established diagnostic criteria. Signs and symptoms of Cytokine release syndrome may include:

- Constitutional – fever, rigors, fatigue, malaise
- Neurologic – headache, mental status changes, dysphasia, tremors, dysmetria, gait abnormalities, seizure
- Respiratory – dyspnea, tachypnea, hypoxemia
- Cardiovascular – tachycardia, hypotension
- Gastrointestinal – nausea, vomiting, transaminitis, hyperbilirubinemia
- Hematology – bleeding, hypofibrinogenemia, elevated D-dimer
- Skin – rash

Subjects may be at an increased risk for cytokine release syndrome during the first few days following the initial infusion of AMG 330. Cytokine release syndrome may be life-threatening or fatal. Infusion reactions may be clinically indistinguishable from manifestations of cytokine release syndrome. Throughout the infusion with AMG 330, monitor subjects for clinical signs (eg, fever, tachycardia, dyspnea, tremors) and laboratory changes (eg, transaminase increase) which may be related to cytokine release syndrome.

Grading and management of cytokine release syndrome should be performed according to the guidelines provided in [Table 7](#) (based on the adopted grading system referenced in Lee et al [Blood 2014]).

**Table 7. Grading and Management of Cytokine Release Syndrome**

CRS Grade	Description of Severity a	Minimum Expected Intervention c	Instructions for Interruption of AMG 330
1	Symptoms are not life threatening and require symptomatic treatment only, eg, fever, nausea, fatigue, headache, myalgias, malaise	

Administer symptomatic treatment (eg, paracetamol/ acetaminophen for fever, fluids for hypotension).

Monitor for CRS symptoms including vital signs and pulse oximetry at least Q2 hours for 12 hours or until resolution, whichever is earlier.

	N/A
2	Symptoms require and respond to moderate intervention  Oxygen requirement < 40%, OR  Hypotension responsive to fluids or low dose of one vasopressor, OR  Grade 2 organ toxicity or grade 3 transaminitis per CTCAE criteria	
Administer:
 

Symptomatic treatment (eg, paracetamol/ acetaminophen for fever; vasopressors for hypotension)

Supplemental oxygen when oxygen saturation is < 90% on room air

Intravenous fluids or low dose vasopressor for hypotension when systolic blood pressure is < 100 mmHg. Persistent tachycardia (eg >120 bpm) may also indicate the need for intervention for hypotension.

Consider use of tocilizumab 8 mg/kg iv. Up to 3 additional doses can be given 8 hours apart, if needed.

 
Monitor for CRS symptoms including vital signs and pulse oximetry at least Q2 hours for 12 hours or until resolution to CRS grade ≤ 1, whichever is earlier.
 
For subjects with extensive co-morbidities or poor performance status, manage per grade 3 CRS guidance below.
	
Institute medical management. If hypotension persists 8 hours after adequate medical management, de-escalate AMG 330 to 50% of the current dose for 24 hours. If symptoms persist, interrupt AMG 330. Refer Section 6.2.1.5 for dose interruption guidelines. If symptoms improve to <= Grade 1, re-escalate to the dose at which the CRS event previously occurred. If symptoms progress to grade 3 criteria, see row below.
 
Permanently discontinue AMG 330 if there is no improvement to CRS ≤ grade 1 within 7 days.

Footnotes defined on next page of table

Page 1 of 2

**Table 7. Grading and Management of Cytokine Release Syndrome**

CRS Grade	Description of Severity a	Minimum Expected Intervention	Instructions for Interruption of AMG 330
3	Symptoms require and respond to aggressive intervention 

• Oxygen requirement <math>\geq 40\%</math>, OR

• Hypotension requiring high doseb or multiple vasopressors, OR

• Grade 3 organ toxicity or grade 4 transaminitis per CTCAE criteria

	Admit to intensive care unit for close clinical and vital sign monitoring per institutional guidelines.  Administer tocilizumab 8 mg/kg iv. Up to 3 additional doses of 8 mg/kg of tocilizumab can be given 8 hours apart, if needed.  Administer dexamethasone (or equivalent) IV at a dose maximum of 3 doses of 8 mg (24 mg/day). The dose should then be reduced step-wise.	Immediately interrupt AMG 330 until event resolves to CRS grade $\leq 1$  Permanently discontinue AMG 330 if there is no improvement to CRS $\leq$ grade 2 within 5 days or CRS $\leq$ grade 1 within 7 days.  Permanently discontinue AMG 330 if CRS grade 3 occurs at the initial run in dose (ie, at MTD1).
4	Life-threatening symptoms 

• Requirement for ventilator support OR

• Grade 4 organ toxicity (excluding transaminitis) per CTCAE criteria

	Admit to intensive care unit for close clinical and vital sign monitoring per institutional guidelines.  Administer dexamethasone (or equivalent) IV at a dose maximum of 3 doses of 8 mg (24 mg/day). Further corticosteroid use should be discussed with the Amgen medical monitor.  Additionally, tocilizumab should be administered at a dose of 8 mg/kg. Up to 3 additional doses can be given 8 hours apart, if needed.	Immediately stop the infusion and permanently discontinue AMG 330 therapy.

Page 2 of 2

CRS, Cytokine Release Syndrome; CTCAE, Common Terminology Criteria for Adverse Events; IV, Intravenous

a Revised grading system for cytokine release syndrome (Lee et al, 2014)

b High dose vasopressors (all doses are required for  $\geq 3$  hours): Norepinephrine monotherapy  $\geq 20$   $\mu$ g/min; Dopamine monotherapy  $\geq 10$   $\mu$ g/kg/min, Phenylephrine monotherapy  $\geq 200$   $\mu$ g/min, Epinephrine monotherapy  $\geq 10$   $\mu$ g/min; If on vasopressin, vasopressin + norepinephrine equivalent of  $\geq 10$   $\mu$ g/min; If on combination vasopressors (not vasopressin), norepinephrine equivalent of  $\geq 20$   $\mu$ g/min

c Investigators may also consider additional therapy, based on clinical judgment.

### Restart of Treatment after Infusion Interruption due to Cytokine Release Syndrome:

After interruption of AMG 330 infusion due to Grade 3 cytokine release syndrome, the infusion may be restarted if all of the following criteria are met:

- The Amgen medical monitor must be consulted prior to restarting treatment
- The event has resolved to grade  $\leq 1$  prior to restarting treatment

If the target dose is █ µg/day, AMG 330 therapy should be restarted at the MTD1 (█ µg/day) for 4 days before step up to an intermediate dose level of █ µg/day. If AMG 330 therapy at █ µg/day is well tolerated for 4 days (ie, absence of grade  $\geq 2$  CRS) then a dose step up to a target dose of █ µg/day can occur.

If the target dose is greater than █ µg/day, AMG 330 therapy should be restarted as described in Section 6.2.1.5. In case of an infusion interruption of  $> 24$  hours, regardless of the reason for interruption, restart of the infusion should be performed at the initial MTD (run in dose) and dose steps should be performed prior to administering the target dose. The dose level for each step and number of steps should be determined in consultation with the Sponsor prior to re-initiation of the infusion.

If a subject experiences 2 separate grade 3 CRS events, AMG 330 must be permanently discontinued.

Please also refer to the general guidance for restart of infusion after interruptions in Section 6.2.1.5.

For Grade 3 and 4 cytokine release syndrome, please see Section 6.2.1.4 for DLT considerations.

### Tumor Lysis Syndrome

Subjects with AML and WBC  $< 10,000/\text{mcl}$  are considered to be at low risk for tumor lysis syndrome. WBC  $> 10,000/\text{mcl}$  and  $< 50,000/\text{mcl}$  are considered to be at intermediate risk, and subjects with WBC  $> 50,000/\text{mcl}$  are considered at high risk. This protocol requires that subjects have a maximum WBC count of 15,000/mcl.

Additional high risk features include baseline uric acid  $> 450 \text{ mcg/L}$  (7.5 mg/dl), serum creatinine  $> 1.4 \text{ mg/dL}$ , and lactate dehydrogenase (LDH) greater than the ULN.

Patients with intermediate risk WBC count and elevated baseline uric acid ( $> 450 \text{ mcg/L}$ ), serum creatinine  $> 1.4 \text{ mg/dl}$ , or LDH greater than ULN will be

recommended to receive allopurinol prophylaxis. Typical dosing is 600-800 mg/day administered bid or qid and should begin 3 days before the first dose of study drug. Patients should be well hydrated and supplemented with intravenous fluid as clinically indicated.

For grade 3 and 4 tumor lysis syndrome, please see Section [6.2.1.4](#) for DLT considerations.

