4.2.18 White blood cells (WBC) > 15,000 cells/mcL at screening

4.2.19 History or evidence of any other clinically significant disorder, condition or disease that, in the opinion of the investigator or Amgen physician, if consulted, would pose a risk to subject safety or interfere with the study evaluation, procedures or completion

4.2.20 Men and women of reproductive potential who are unwilling to practice a highly effective method(s) of birth control while on study through 1 week (women) or 12 weeks (men), respectively, after receiving the last dose of study drug. Acceptable methods of highly effective birth control include

sexual abstinence (men, women); vasectomy; bilateral tubal ligation/occlusion; or a condom with spermicide (men) in combination with hormonal birth control or intrauterine device (IUD) (women)

- 4.2.21 Women who are lactating/breastfeeding or who plan to breastfeed while on study through 1 week after receiving the last dose of study drug
- 4.2.22 Women with a positive pregnancy test
- 4.2.23 Women planning to become pregnant while on study through 1 week after receiving the last dose of study drug
- 4.2.24 Subjects likely to not be available to complete all protocol-required study visits or procedures, and/or to comply with all required study procedures to the best of the subject and investigator's knowledge

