  - $\pm$  1 day window if collected at D8 or later, or at the EOI.

- Bone marrow assessments post treatment start: +/- 3 days
- PK blood draws in cycles 1 - 3:
  - within two hours prior to treatment start / dose step (if applicable )
  - $\pm$  15 minute window for samples taken within the first 24 hours after start of infusion and within 24 hours after EOI. In case of a dose step, the  $\pm$  15 minute window also applies to the samples taken within the first 24 hours after dose step.

Local laboratories should be used for the following assessments: hematology, hematological bone marrow assessments, clinical chemistry, coagulation, urinalysis, hepatitis serology, and serum pregnancy tests. The following collections will be shipped to a central laboratory for analysis: blood samples for determination of plasma concentrations of AMG 330 and anti-AMG 330 antibodies, as well as blood and bone marrow samples for biomarker assessment and biomarker development. Refer to the laboratory manual for detailed collection, processing, and shipping procedures.

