**Table 24. List of Analytes**

Chemistry	Hematology	Urinalysis	Coagulation	Other Labs
Sodium	Erythrocytes	Specific gravity	PT	Pregnancy test a
Potassium	Hemoglobin	pH	PTT	Serology (HepB, HepC)
Bicarbonate	Hematocrit	Blood	INR	
Or	MCV	Protein	Fibrinogen	MRD (for subjects with <5% blasts in bone marrow; Groups 1 and 2)
Total CO 2	Platelets	Glucose	AT III	
Chloride	WBC Differential	Bilirubin		
Total protein	Total Neutrophils	Ketones		
Albumin	Seg. Neutrophils	Microscopic exam		
Adjusted	Lymphocytes	(performed at the discretion of the investigator)		
Calcium	Atypical Lymphocytes			
Magnesium	Monocytes			
Phosphorus	Bands/Stabs			
Glucose	Eosinophils			
Creatinine	Basophils			
Total bilirubin	Blasts			
ALP	Myeloblasts			
AST	Monoblasts			
ALT	Megakaryoblasts			
GGT	Promyelocytes			
Amylase	Myelocytes			
Lipase	Metamyelocytes			
CRP	Nucleated RBC			
LDH	Immature			
Uric Acid	Granulocytes			
Ferritin				

ALP = alkaline phosphatase; ALT = alanine aminotransferase; anti-HBc = Hepatitis B core antibody; AST = aspartate aminotransferase; AT III = Antithrombin III; CRP = C-reactive protein; **GGT = gamma-glutamyl transferase**; HepBsAg = hepatitis B surface antigen; HepCAB = hepatitis C antibody; INR = international normalize ratio; LDH = lactate dehydrogenase; MCV = mean corpuscular volume; PT = prothrombin time; PTT = partial thromboplastin time; WBC = white blood cell

a Serum pregnancy test will be performed for all females unless surgically sterile or ≥ 2 years postmenopausal.

Additional procedures (eg collection of an unscheduled blood sample to measure cytokine levels) deemed necessary as part of standard of care or as required by local laws and regulations may be performed at the investigator's discretion.

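### Protocol Section 6.6 prints the uric acid threshold as 450 mcg/L and 7.5 mg/dl, which differ 167-fold; the allopurinol sentence carries only the mcg/L figure

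*Protocol*

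**What the plan says.** The text is in Protocol Section 6.6, "Specific Recommendations for Cytokine Release Syndrome, Tumor Lysis Syndrome and Infection Prophylaxis", under Tumor Lysis Syndrome. Subjects are first graded by white cell count: low risk below 10,000/mcL, intermediate from 10,000 to 50,000, high above 50,000. The section then adds other markers: "Additional high risk features include baseline uric acid" above 450 mcg/L, creatinine above 1.4 mg/dL, and LDH above the upper limit of normal. The bracketed equivalent for uric acid can be seen in "7.5 mg/dl), serum creatinine".

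The next paragraph is the one that leads to action. It begins "Patients with intermediate risk WBC count and elevated baseline uric acid", gives the cut-off in brackets as above 450 mcg/L with no mg/dL figure, and joins it by 'or' to the same creatinine and LDH criteria. Patients who qualify are "recommended to receive allopurinol prophylaxis", typically 600-800 mg/day, starting 3 days before the first dose of study drug.

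No other section gives a uric acid threshold. "Table 24. List of Analytes" names uric acid without a unit. Section 7.2 sends chemistry to the sites' own laboratories: "Local laboratories should be used for the following assessments: hematology, hematological bone marrow assessments, clinical chemistry".

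**The concern.** The protocol offers the two figures as the same threshold, and they are not. The sentence that tells a site when to recommend treatment carries only the mcg/L figure. With local laboratories and no unit in the analyte table, Section 6.6 is the only place in the protocol from which a site can take the cut-off.

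Taken at face value, the uric acid criterion would stop discriminating. Allopurinol would then be recommended to subjects with an intermediate white cell count and none of the additional markers. The amendment log says that provisions for identifying subjects at high risk of tumor lysis syndrome were added at the FDA's request, so a threshold included for that purpose should be consistent with itself.

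**Working it through.** **Inputs, all from Protocol Section 6.6 except the last**

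- Uric acid threshold, list of additional markers: > 450 mcg/L, with 7.5 mg/dl in brackets.
- Uric acid threshold, allopurinol paragraph: > 450 mcg/L only.
- Intermediate-risk white cell count: 10,000 to 50,000/mcL.
- Upper limit on white cell count at entry: exclusion 4.2.18, "White blood cells (WBC) > 15,000 cells/mcL at screening".

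**Step 1. Try to reproduce the printed equivalence, using metric prefixes only**

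- 450 mcg/L ÷ 1,000 = 0.45 mg/L; ÷ 10 = 0.045 mg/dL. The plan prints 7.5 mg/dl, so the equivalence is not reproduced.
- In reverse: 7.5 mg/dL × 10 = 75 mg/L; × 1,000 = 75,000 mcg/L.

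**Step 2. Size of the discrepancy**

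- 75,000 / 450 = 166.7, about 167-fold.
- 0.045 / 7.5 = 0.006, so the literal cut-off is 0.6% of the bracketed one.

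**Step 3. What the literal cut-off would do**

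A uric acid of 0.75 mg/dL, one tenth of the bracketed threshold, is 0.75 / 0.045 = 16.7 times the literal cut-off. That practically any measured value exceeds 0.045 mg/dL is a general clinical judgment; the documents give no reference range.

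**Step 4. Could a nearby unit explain the pair?**

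- 450 mcg/dL = 0.45 mg/dL: no.
- 450 mg/L, or equally 450 mcg/mL, = 45 mg/dL: no.
- 450 micromol/L, with a molar mass for uric acid of 168.11 g/mol: 450 × 168.11 / 10,000 = 7.57 mg/dL. This fits to rounding; in reverse, 7.5 mg/dL is 75,000 / 168.11 = 446 micromol/L.

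The molar mass is an outside constant, and the protocol does not name this unit. Step 4 suggests what was intended. The conflict itself rests on Steps 1 and 2 alone.

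**Step 5. Who would be handled differently**

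Because the criteria are joined by 'or', a subject with creatinine above 1.4 mg/dL or LDH above normal already qualifies. The literal reading changes the advice only for subjects who meet all of these:

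- WBC 10,000 to 15,000/mcL
- creatinine at or below 1.4 mg/dL
- LDH not above the upper limit of normal
- uric acid above 0.045 but not above 7.5 mg/dL

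All of them are intermediate risk by white cell count already. The documents give no count for this subset.

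**The case against.** The strongest reply is that the text largely corrects itself. The usable 7.5 mg/dl stands just before the allopurinol paragraph, that paragraph says the uric acid must be elevated, and a clinician would read the two together. The wording is advisory, and Section 6.5 lets investigators give supportive care as they judge necessary, so access to allopurinol does not hang on this number. Tumor lysis syndrome counts toward a DLT by grade, clinical management and resolution (Section 6.2.1.4), not by this cut-off. All of that stands, and it is why the weight is low.

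Two further points concern certainty. First, prefixes show that the figures conflict, not which one is right. That is true as logic, but 0.045 mg/dL cannot sensibly mark an elevated value, and the micromol/L correction is left to the sponsor's confirmation. Second, the text was read from PDF and the page image is not available, so a misread unit cannot be fully excluded. The same unit appears in two separate sentences, which makes a single misread character unlikely, although a systematic misreading would repeat.

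It can also be argued that this is merely editorial. It is more than a background typo, because it sits in operative text that sets a treatment threshold.

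**Conclusion.** The concern holds. The two printed figures contradict each other by a factor of 167, and the sentence that triggers the recommendation carries only the figure that makes no clinical sense. The practical effect is small. It needs a site to take the unit literally, it concerns only the subset in Step 5, and it leads to more prophylaxis rather than less. Eligibility, sample size, endpoints and the planned analyses are untouched. This is a unit correction that should be made, not a safety gap.

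The contradiction needs no assumption beyond accurate text extraction. The statement that practically any value would qualify rests on general clinical knowledge, and the suggestion that micromol/L was intended rests on the molar mass.

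**What to change.** State the threshold as > 7.5 mg/dL in both sentences and remove the mcg/L figure. This uses a value the protocol already prints and matches the mg/dL unit used for creatinine beside it. Alternatively, once the sponsor confirms the intended unit, print > 450 micromol/L (7.5 mg/dL) in both places.

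The cost is two unit corrections in one subsection. SAP Section 10 already anticipates Protocol Amendment 10, which can carry them. No separate letter to sites is needed.

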#### Infection Prophylaxis

Subjects who may experience neutropenia for 7 days or longer are at a high risk for infectious complications. As appropriate, these subjects should be administered prophylactic antibacterial (eg, fluoroquinolones), antifungal and antiviral medications. These subjects should be monitored for early signs of breakthrough infections after the initiation of antibacterial therapy to prompt additional evaluation and possible therapy modification.

#### **6.7 Medical Devices**

The investigational product must be administered using infusion pumps approved for use by the appropriate regulatory authorities for the country in which the subject is undergoing treatment in both the inpatient and outpatient setting. Investigational product infusion for solution will be prepared in bags for IV infusion and delivered through infusion lines with a 0.2 µm in-line filter that are both compatible with the investigational product as described in the IPIM.

Additional details for the use of the above mentioned medical devices and specific set of device specifications are provided in the IPIM.

Additional medical devices (eg, syringes, sterile needles, alcohol prep pads), that are commercially available are not provided or reimbursed by Amgen (except, if required by local regulation). The investigator overseeing the conduct of the study at each respective institution will be responsible for obtaining these supplies.

